8.2. Expected Adverse Reactions

In clinical trials, observed adverse effects of Antroquinonol are summarized as following:

- Diarrhea (92.31%)
- Vomiting (69.23 %)
- Nausea (53.85 %)

If a GI event occurs, adequate drugs/therapies could be administered based on investigator's judgements. If the event is judged as grade 3 according to CTCAE v4.03, this event will be seen as a serious adverse event.

8.3. Serious Adverse Events (SAE)

An SAE is any adverse event/experience occurring at any study drug dose that results in any of the following outcomes:

- Death
- Life-threatening (defined as an event in which the subject is at immediate risk of death at the time of the event; life-threatening does not refer to an event that hypothetically might have caused death if it were more severe, resulting in permanent or significant disability/incapacity)
- Requires inpatient hospitalization or prolongation of existing inpatient hospitalization (excluding the hospitalization for the protocol specified image taking)
- Results in congenital anomaly or birth defect
- Results in persistent or significant disability or incapacity
- Events requiring medical and/or surgical intervention to prevent permanent impairment of function or permanent damage to a body structure

All SAEs will be:

- recorded on the appropriate SAE CRF
- followed through resolution by a study clinician
- reviewed and evaluated by a study clinician

An adverse event would meet the criterion of "requires hospitalization", if the event necessitated an admission to a health care facility (e.g., overnight stay). Hospitalization does not include the following:

- Rehabilitation facilities
- Hospice facilities
- Respite care (e.g., caregiver relief)

- Skilled nursing facilities
- Nursing homes

Hospitalization or prolongation of hospitalization is not in itself an SAE. Examples include:

- Admission for treatment of a preexisting condition not associated with the development of a new adverse event or with a worsening of the preexisting condition (e.g., for work-up of persistent pretreatment lab abnormality)
- Administrative admission (e.g., for yearly physical exam)
- Protocol-specified admission during a clinical trial (e.g., for a procedure required by the trial protocol)
- Preplanned treatments or surgical procedures should be noted in the baseline documentation for the entire protocol and/or for the individual subject

The study will adhere to the full requirements of the ICH Guideline for Clinical Safety Data Management, Definitions and Standards for Expedited Reporting, Topic E2 and comply with local regulatory requirements.

8.4. Reporting Procedures

8.4.1. Reporting procedures for AEs and SAEs

All AEs and SAEs must be documented in the source documents and the relevant CRF and ADR form when applicable. The investigator may be asked to provide photocopies of the medical records for completion of AE or SAE report. The subjects' names on the medical records submitted to the relevant parties will be concealed. It is the investigator's responsibility to record AEs and SAEs by diagnosis terminologies, if possible. When the diagnosis is not possible for AE or SAE recording/reporting, signs and symptoms will be used for reporting instead.

According the amended provision 106 of "Good Clinical Practice" (2010, by Department of Health, Taiwan), serious adverse events that are unexpected (i.e., SAEs that are not identified or recorded on protocol Section 8.3, investigator brochure and ICF) and related or possibly related to study drugs must be immediately reported to the "National Reporting System of Adverse Drug Reaction in Taiwan" using Adverse Drug Reaction (ADR) forms, which will be completed by the investigator. A copy of the ADR form will be filed in the site files. Those SAEs that are unexpected and related or possible related to study drugs should also be reported to local Research Ethics Committees (REC) according to its regulations.

When any mentioned event happens to a subject between the times a participant signs the informed consent form and the time a subject departs the study at the end of the final visit should be reported to ADR center and local REC. All new serious adverse events occurring

beyond this time frame and coming to the attention of the investigator must be recorded only if they are considered (based on the investigator's opinion) causally-related to the study drug. It is very important that the investigator should take information of underlying diseases, concomitant drugs, temporal relationship of the onset of the event to the time of dosing the study drugs, and re-challenging outcomes, into account when the investigator is making a causal relation decision (as described in **Section 8.1**).

It is also investigator's responsibility to proactively follow the outcome of each AE/SAE until resolution or stabilization of the condition or loss of follow-up. **Serious, alarming and/or unusual adverse** events must be reported to local Research Ethics Committees (REC) within 24 hours of the investigator's knowledge of the event.

An ADR form should be completed for all SAEs that are **unexpected and related or possibly related** to study drugs (SUSARs, suspected unexpected serious adverse reactions) and forwarded to the ADR center and the REC in according to the requirements of the institutions. Investigators should follow subjects as far as possible until an outcome of the events is known. The investigator will notify health authority of all the SAEs that are "death" or "life-threatening" in 7 calendar days, followed by a report within additional 8 calendar days. All of the remaining SAE events should be reported to health authority within 15 calendar days. The copy of each report will be kept in investigator's files. Also, the investigator must inform SAE to local REC within the time frame regulated by REC.

Lastly, all AEs, regardless of severity, will be followed by the investigator until the resolution is satisfactory. All the information must be collected on the action taken with the study drug.

Serious, alarming and/or unusual adverse events must be reported to the following individuals within 24 hours of the investigator's knowledge of the event:

AFFILIATION	DEPARTMENT	TELEPHONE NUMBER	FAX NUMBER
Bestat Pharmaservices Corp.	Clinical Research	[name]	[name]

8.4.2. Reporting pregnancy

If a pregnancy occurs in a female subject while the subject is taking protocol-required therapies, subject pregnancy must be reported by the investigational staff within 24 hours of their knowledge. If a pregnancy occurs in a female partner of a male subject, while the subject is taking protocol-required therapies, it will be reported by the investigational staff within 24

hours of their knowledge. Any subject who becomes pregnant during the study must be promptly withdrawn from the study. Follow-up information regarding the outcome of the pregnancy and any postnatal sequelae in the infant will be required. The investigational staff shall record pregnancy on adverse event page on CRF, fill in an ADR form and inform both Sponsor and CRO designee aforementioned.

9. STATISTICAL CONSIDERATIONS AND ANALYTICAL PLAN

9.1. Study Hypothesis

Several hypotheses will be tested regarding the lipid change to determine if the benefits of Antroquinonol in the context of desirable levels of primary endpoint TG, and secondary endpoint TC, HDL-C, LDL-C, and LDL/HDL ratio. As well as the effect of Antroquinonol on E/E', baPWV and ABI and HU parameters.

9.2. Sample Size Considerations

The primary efficacy endpoint in this trial is “to compare the percentage change of triglyceride (TG) from baseline following a 12-week regimen of Antroquinonol versus placebo.” The objective of this trial is to assess the efficacy of the study treatment compared with control treatment. According to the literature review (FDA statistical reviews of Fibrate), the TG reduction percentage change of Fibrate from baseline to last visit was 36.6% for subjects who were treated with the study treatment, and 0.7% increased for the control treatment. According to prior published clinical reference, it is assumed that the mean TG percentage reduction is 27.5% and standard deviation is 40. The evaluable patient number should be at least 24 patients for each group under one-sided significance level 0.025 and power 90%. Considering a 20% drop-out rate, a sample size of 30 patients should be enrolled to each group, and a total of 120 patients will be recruited into this study. The sample size calculation was derived using PASS 2008.

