## **5 SAMPLE SIZE DETERMINATION**

The sample size estimation of this study is using two-sample T-test under one-sided significance level 0.025, power 90%. Based on the Davidson's study, the TG reduction percentage change of 130 mg Fenoribrate from baseline to last visit was 36.6% for subjects who were treated with the study treatment, and the standard deviation was 2.4% and 5.3% for the study treatment and the control treatment. Assuming a drop-out rate of 20%, a sample size of 120 patients (30 patients per arm) were required to provide 96 evaluable patients (24 patients for each group) which indicates an achievement of 80% completion rate.

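### Protocol 9.2: a 27.5-point difference from placebo with a per-arm SD of 40 gives about 64% power at 24 per group, not 90%; SAP 5 rests the same 24 on different figures

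*Protocol*

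**What the plan says.** Protocol 9.2 defines the comparison being sized as "to compare the percentage change of triglyceride (TG) from baseline following a 12-week regimen of Antroquinonol versus placebo". It cites a fibrate result in which the TG reduction "was 36.6% for subjects who were treated with the study treatment, and 0.7% increased for the control treatment". It then turns to a separate published reference: "it is assumed that the mean TG percentage reduction is 27.5% and standard deviation is 40". From this it concludes that "The evaluable patient number should be at least 24 patients for each group under one-sided significance level 0.025 and power 90" per cent. A 20% drop-out allowance takes this to 30 per group and 120 in total. The section adds: "The sample size calculation was derived using PASS 2008".

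SAP 5 names the test: "The sample size estimation of this study is using two-sample T-test under one-sided significance level 0.025, power 90" per cent. It does not mention 27.5 or 40. It cites a fenofibrate study with a 36.6% reduction on active treatment and says "the standard deviation was 2.4% and 5.3% for the study treatment and the control treatment". It gives no mean change for the control arm. It reaches the same number: 120 patients "were required to provide 96 evaluable patients (24 patients for each group"). SAP 12 declares no change to the protocol, statistical or otherwise.

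**The concern.** For a parallel-group comparison with placebo, the effect in a two-sample t-test is the difference between arm means, and the SD is the spread of individual patients within an arm. Put into that test, 27.5 and 40 give a standardised difference of 27.5/40 = 0.69. Twenty-four per group is too few for 90% power at that size.

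The power statement tells the reader how to take a non-significant primary result. At 90%, the trial would miss the assumed effect one time in ten. At 64.5%, it would miss it more than one time in three. The SAP adds a second, incompatible set of inputs for the same 24, so a reader of both documents cannot tell which effect the trial was sized to detect.

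**Working it through.** **Inputs.** One-sided alpha 0.025, power 90%, 24 evaluable per group, effect 27.5 and SD 40 (Protocol 9.2); two-sample t-test (SAP 5); 1:1:1:1 allocation (Protocol 4.5.1); 20% drop-out (Protocol 9.2).

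**Drop-out step.** 24/0.8 = 30 per group, and 30 × 4 = 120. This reproduces and is not in question.

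**Reproducing the 24 with difference 27.5 and per-arm SD 40.** Power comes from the noncentral t distribution with 2n − 2 degrees of freedom and noncentrality δ/(σ√(2/n)).

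- At n = 24: 27.5/(40 × √(2/24)) = 2.38, df 46, critical t 2.013, power **64.5%**.
- At n = 30 (nobody drops out): 74.5%.
- At n = 45: 89.7%. At n = 46: 90.4%. So 90% needs **46 per group**. The normal approximation 2 × (40 × (1.960 + 1.282)/27.5)² = 44.5, rounded up to 45, agrees closely.
- For 90% power at 24 per group, the difference would have to be about 38.2 points with SD 40, or the per-arm SD about 28.8 with a difference of 27.5.

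**Other ways of reading Protocol 9.2** (one-sided 0.025):

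| Effect | SD, as used | Power at 24 | n for 90% |
|---|---|---|---|
| 27.5 + 0.7 = 28.2 | 40 per arm | 66.7% | 44 |
| 36.6 | 40 per arm | 87.3% | 27 |
| 36.6 + 0.7 = 37.3 | 40 per arm | 88.5% | 26 |
| 27.5 | 40 for the difference between two patients (40/√2 = 28.3 per arm) | 90.9% | 24 |
| 27.5 | 40, one-sample test within one arm | 89.7% | 25 |

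Only the fourth row gives 24 as the smallest n reaching 90% (23 gives 89.7%). The fifth comes close but is not a comparison with placebo.

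**SAP 5 figures.** The root-mean-square of the two SDs is √((2.4² + 5.3²)/2) = 4.11. With that SD, 24 per group gives 90% power for a difference of only about 3.9 points; with 5.3 in both arms, about 5.1 points. A 36.6-point difference would need about 2 per group. For these figures to yield 24, placebo would have to fall by about 36.6 − 5.1 = 31.5 to 36.6 − 3.9 = 32.7 points, whereas Protocol 9.2 reports a 0.7% rise on control.

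**The case against.** The strongest reply is that this is a missing label and not a wrong calculation. Protocol 9.2 never calls 40 a per-arm SD. Reading it as the SD of a between-patient difference returns exactly 24, and an exact match suggests that the software run may have been right. The 37.3-point literature difference with SD 40 also comes close by normal approximation (unrounded n 24.2, power 89.8% at 24). This stands as far as it goes: 90% is not shown to be wrong on every reading. But neither document states the reading that works, and the SD quoted for a two-sample t-test is ordinarily the per-arm SD. On the 37.3 reading, the 27.5 that the protocol says it assumed would play no part.

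A second reply is that the primary analysis in SAP 9.3 is a four-group ANCOVA with baseline TG as covariate, not an unadjusted t-test. SAP 5 nevertheless sizes on the t-test. To bring an SD of 40 down to 28.8, baseline TG would need a correlation with percentage change of √(1 − (28.8/40)²) ≈ 0.69, and no such value is assumed. The overall test does not restore 90% either: with all three doses at 27.5, placebo at 0, SD 40 and no gain from the covariate, its power is about 66%.

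Third, SAP 5 presents 36.6%, 2.4% and 5.3% as results of another study, not explicitly as planning values, and SAP 12 may be meant to cover only the analyses. Both are fair. The placebo fall of about 32 points is therefore only an illustration. It remains that SAP 5 offers these as the basis for the 24 and gives no other inputs.

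Finally, the trial is Phase II with no interim analysis, the correction changes no patient number, and the planned confidence intervals help in reading a null result. That makes the correction cheap but does not make the power statement right.

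**Conclusion.** The concern holds. With 27.5 as the difference from placebo, 40 as the per-arm SD and an unadjusted two-sample t-test at one-sided 0.025, 24 per group gives 64.5% power. The chance of missing the assumed effect is 35.5%, against the 10% stated, and 90% power needs 46 per group. None of the other placebo comparisons that can be formed from Protocol 9.2 with a per-arm SD of 40 reaches 90% at 24. The stated power stands only if the per-arm SD was about 28.3, which the text does not say.

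The disagreement between Protocol 9.2 and SAP 5 does not depend on how 27.5 and 40 are read: the two sections justify one sample size with incompatible inputs, and those in the SAP do not lead to 24 for any effect the documents give.

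As a side note, at the 0.05/5 level in SAP 9.7 the 27.5-point comparison with per-arm SD 40 has about 39% power. SAP 7.7 also plans pairwise t-tests at an unadjusted 0.05, so this is not the only threshold in play.

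**What to change.** Keep 120 patients. Recover the inputs from the PASS 2008 run and give one set in both Protocol 9.2 and SAP 5: between-group difference, per-arm SD, test and alpha. Then restate the power according to what the run shows.

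- **27.5 is the difference and 40 the per-arm SD:** say that 24 evaluable patients per group give about 64% power for a 27.5-point difference from placebo in an unadjusted two-sample t-test at one-sided 0.025, and that 90% power requires a difference of about 38 points.
- **40 is the SD of a difference between two patients:** state the per-arm SD of about 28.3 and justify it; the power is then about 91%.
- **27.5 is a fall within the active arm:** add the assumed placebo change and recompute.

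In SAP 5, remove the 2.4% and 5.3% SDs or reconcile them with the protocol, and state the control-arm change assumed. Power at the 0.05/5 level could be added for information.

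The cost is wording in two sections and, on the usual reading, a less favourable power statement. No test, estimate or patient number changes.

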9.3. Analyzed Population

There will be three populations in this study, Intent-To Treat (ITT) population, Per-Protocol (PP) population and Safety populations for statistical analysis. Primary efficacy analysis will be performed in both ITT and PP population, while secondary efficacy analyses will be performed in ITT population only. Safety population will be used in analysis of safety variables. The populations for analysis applied into this study are defined as following:

Intent to Treat Population (ITT):

The ITT population includes all randomized patients who meet all inclusion criteria and exclusion criteria, take at least one study medication and have at least one post-baseline

measurement.

Per-Protocol Population (PP):

The PP population is a subset of the ITT population and includes all randomized patients who complete 12 weeks of treatment without major protocol violation.

The definition of major protocol violations include (1) violate the enrollment criteria, (2) use prohibited medications indicated to treat dyslipidemia, and (3) drug compliance less than 70%.

Safety Analysis Population:

All subjects who received at least one study medication will be included in the safety analysis population.

9.4. Analysis Plan

General data analysis

For continuous endpoints, descriptive statistics including number, mean, median, standard deviation, minimum, maximum, and 95% confidence intervals will be presented. Continuous variables will be analyzed by means of ANOVA with Bonferroni adjustment. Paired T-Test will be used to compare the change from baseline within treatment groups. If the data strongly indicate a violation of the normal assumption, the non-parametric method of Kruskall Wallis test or Wilcoxon Signed-Rank Test will be applied for analysis.

For categorical endpoints, the count and percentages will be used to summarize the categorical data. The Chi-square test will be performed to test the difference between groups while Fisher's exact test will be applied for any counting of the frequency is less than 5.

All statistical analyses will be conducted using SAS software.

Endpoints

The primary efficacy endpoint for assessing the superiority of Antroquinonol to placebo will be analyzed using analysis of covariance (ANCOVA) model and baseline measurement as covariates, if the differences in baseline characteristics, such as gender, age, weight etc., are observed, for comparing the effectiveness between the treatment groups.

Analysis of other secondary efficacy endpoints (TC, HDL-C, LDL-C, and LDL/HDL ratio as well as the effect of Antroquinonol on E/E', baPWV and ABI and HU parameters) will be similar to the primary analysis of the primary endpoint. All tests will be based on a significance level of 0.05, without adjustment for multiple endpoints.

For the safety assessments, the information of adverse events will be described in detail. Count

and percentage will be tabulated for the number of patients with AEs, number of total AEs, number of patients with AEs associated to study dosing and intensity. Adverse events will be coded by the Medical Dictionary for Regulatory Activities (MedDRA®) adverse event dictionary. All the AEs will be categorized by each represented Preferred Terms (PT) and System Organ Class (SOC), which will be tabulated by body system with related incidence rates. The clinical laboratory tests and electrocardiogram tests will be analyzed to separate subjects into normal and abnormal categories, with number of subjects and percentage of subjects in each category, and McNemar's test or Fisher's exact test will then be applied to test the changes between each visit.

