- The ITT population includes all randomized patients who meet all inclusion criteria and exclusion criteria, take at least one study medication and have at least one post-baseline measurement
- The PP population is a subset of the ITT population and includes all randomized patients who complete 12 weeks of treatment without major protocol violation.
- All subjects who received at least one study medication will be included in the safety analysis population.
- Primary efficacy analysis will be performed in ITT and PP population, secondary efficacy analyses will be performed in ITT population and safety analyses will be performed using safety population.
- Last observation carried forward (LOCF) will be used to approach the missing data of primary endpoint in ITT population. No missing data will be imputed for the secondary efficacy or safety analyses.
- Descriptive statistics will be summarized as n, mean, standard deviation, median and range for continuous parameters, and will be tabulated as frequency and percentage for categorical parameters.
- To compare TG percentage change from baseline to week 12 between 3 treatment groups, the ANOVA with

Bonferroni adjustment will be performed, or if assumption of normality is not met, then Kruskal-Wallis Test will be performed. If the differences in baseline characteristics, such as gender, age, weight etc., are observed, the ANCOVA will adjust for the significant variables in the primary analysis. The within-group change from baseline in each treatment group will be assessed using the paired-T test. If the normal assumption is violated, Wilcoxon signed-rank test will replace the paired-T test.

- Other continuous variable at each visit and change at post-baseline visits will be summarized by descriptive statistics and be analyzed by means of ANOVA with Bonferroni adjustment. Paired T-Test will be used to compare the change from baseline within treatment groups. If the normal assumption is violated, non-parametric statistical methods such as Kruskal-Wallis Test or Wilcoxon Signed-Rank Test will be used.
- Categorical variables will be tabulated with related frequency and percentages and be compared by using Chi-square or Fisher's exact test.

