## 9.4 Secondary Endpoint Analyses

Analysis of other secondary efficacy endpoints (TC, HDL-C, LDL-C, and LDL/HDL ratio as well as the effect of Antroquinonol on E/E', baPWV and ABI and HU parameters) will be similar to the primary analysis of the primary endpoint by using ANCOVA model using baseline measurement as covariates, or using Kruskal-Wallis test when normal assumption is violated. Pairwise comparison will use two independent t-test or Wilcoxon rank-sum test, and performed significance level of 0.05 while statistical significance of ANCOVA or Kruskal-Wallis test treatment effect is achieved (Antroquinonol 50 mg vs. Placebo, Antroquinonol 100 mg vs. Placebo, Antroquinonol 150 mg vs. Placebo, Antroquinonol 100 mg vs. Antroquinonol 50 mg and Antroquinonol 150 mg vs. Antroquinonol 100 mg).

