## 12 SUMMARY OF CHANGES TO THE PROTOCOL

No change in non-statistical and statistical analysis to the protocol.

Protocol: GHLIP-2-001

Study Sponsor: Golden Biotechnology Corporation

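### SAP 9.4 tests five dose pairs per secondary endpoint at unadjusted 0.05 where the protocol prescribes Bonferroni adjustment, and SAP 12 declares no change

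*Protocol*

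**What the plan says.** **Protocol.** Section 9.4, under general data analysis, states: "Continuous variables will be analyzed by means of ANOVA with Bonferroni adjustment". The statistical methodology part of the protocol summary sets ANOVA with Bonferroni for TG, then says that the other continuous variables will be "summarized by descriptive statistics and be analyzed by means of ANOVA with Bonferroni adjustment". For the secondary endpoints, section 9.4 asks for an analysis similar to the primary one and adds: "All tests will be based on a significance level of 0.05, without adjustment for multiple endpoints". The protocol does not give the number of comparisons to divide by, and its Kruskal-Wallis fallback mentions no adjustment.

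**SAP.** Section 9.4 says of the secondary endpoints: "Pairwise comparison will use two independent t-test or Wilcoxon rank-sum test, and performed significance level of 0.05 while statistical significance of ANCOVA" or Kruskal-Wallis is reached. It lists five pairs: each dose against placebo, plus "Antroquinonol 100 mg vs. Antroquinonol 50 mg and Antroquinonol 150 mg vs. Antroquinonol 100 mg". Section 7.7 describes Bonferroni as the correction for the primary endpoint. Section 9.7 gives 0.05/m with m = 5 and refers to section 9.3, the TG analysis. Section 12 states: "No change in non-statistical and statistical analysis to the protocol".

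**The concern.** Two kinds of multiplicity are involved. One is across the eight secondary endpoints (TC, HDL-C, LDL-C, LDL/HDL ratio, E/E', baPWV, ABI, HU), which the protocol openly leaves uncorrected. The other is across dose pairs within one endpoint, which its Bonferroni sentences address. SAP 9.4 drops the second correction, and SAP 12 does not list that as a change.

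With four arms, a significant omnibus test protects the pairwise tests only while all arms are equal. Once one dose shifts a lipid, the gate tends to open and the ineffective doses are then compared at 0.05 each. At stake is which doses are called effective on LDL-C, HDL-C and the rest. SAP 2 intends these analyses for regulatory submission and manuscripts, SAP 9.7 declares significance whenever p is below the test's level, and nothing labels the secondary results as descriptive.

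**Working it through.** **Step 1: the texts side by side.**

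| Question | Protocol | SAP |
|---|---|---|
| Dose pairs within a non-primary continuous endpoint, parametric | Bonferroni (9.4, summary) | 0.05 per pair after the gate (9.4) |
| The same, after Kruskal-Wallis | Silent | 0.05 per pair after the gate (9.4) |
| Across endpoints | No adjustment (9.4) | No adjustment stated |
| Declared change | – | None (12) |

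Only the first row is an explicit conflict.

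**Step 2: the plan's own figure.** Neither document states an error rate for the secondary pairs. The one relevant figure is m = 5 in SAP 9.7, so 0.05/5 = 0.01 per test.

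**Step 3: how many listed pairs are null when one dose works.**
- Only 150 mg works: 50 vs placebo, 100 vs placebo, 100 vs 50. Three null pairs.
- Only 50 mg works: 100 vs placebo, 150 vs placebo, 150 vs 100. Three null pairs.
- Only 100 mg works: 50 vs placebo, 150 vs placebo. Two null pairs.

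With the gate fully open, the upper bound with three null pairs is 3 × 0.05 = 15% unadjusted, 3 × 0.05/3 = 5% at 0.05/3, and 3 × 0.01 = 3% at 0.05/5. With two null pairs it is 10%, 3.3% and 2%. Pairs that share an arm are correlated, so the true rates are somewhat lower.

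**Step 4: simulation with the gate.** Inputs from the documents: four arms at 1:1:1:1 (Protocol 4.5.1), 24 evaluable or 30 enrolled per arm (Protocol 9.2), two-sided 0.05 (SAP 7.12), and the five pairs of SAP 9.4. Assumptions: normal data with equal variance, an ANOVA F-test standing in for the ANCOVA gate, and effect sizes of 0.25 to 1.5 SD. The value 27.5/40 = 0.6875 SD is borrowed from the TG design in Protocol 9.2. Each setting has 200,000 trials, with a simulation error below 0.1 percentage point. The table gives the chance (%) of at least one rejection among the null pairs of one endpoint.

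| n per arm | Active dose, effect | 0.05 per pair | 0.05/3 | 0.05/5 |
|---|---|---|---|---|
| 24 | none | 4.9 | 4.1 | 3.3 |
| 24 | 150 mg, 0.25 SD | 5.5 | 3.2 | 2.3 |
| 24 | 150 mg, 0.5 SD | 9.3 | 4.0 | 2.6 |
| 24 | 150 mg, 0.6875 SD | 11.3 | 4.4 | 2.7 |
| 24 | 150 mg, 1.5 SD | 12.3 | 4.4 | 2.7 |
| 24 | 100 mg, 0.25 SD | 4.4 | 2.3 | 1.6 |
| 24 | 100 mg, 0.6875 SD | 8.4 | 3.1 | 1.9 |
| 24 | 100 mg, 1.5 SD | 9.0 | 3.0 | 1.9 |
| 30 | 150 mg, 0.25 SD | 5.9 | 3.3 | 2.4 |
| 30 | 150 mg, 0.6875 SD | 11.7 | 4.3 | 2.6 |

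With 50 mg as the active dose, the results match those for 150 mg. The 0.05/3 column is there because the protocol gives no divisor.

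**The case against.** **The protocol is itself ambiguous.** The sentence specific to secondary endpoints puts all tests at 0.05, and SAP 9.4 can be read as following it. That reading is possible, but the sentence goes on to limit the waiver to multiple endpoints. Stretching it to dose pairs would cancel the Bonferroni sentence in the same section and the one on other variables in the summary. The ambiguity is a reason to clarify the rule, not to leave it.

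**SAP 9.7 may be general.** Its mention of section 9.3 might only show where the 5 comes from, and SAP 9.4 lists the same five pairs. Section 7.7 names the primary endpoint, which favours the narrower reading. If 9.7 is general, the SAP contradicts itself and needs the same correction.

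**The rank-based branch.** The protocol attaches Bonferroni to ANOVA only, so after Kruskal-Wallis the SAP contradicts nothing. This stands.

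**The size.** A reader might infer a fixed multiple, such as a fourfold rise. At n = 24 and 0.6875 SD with 150 mg active, 11.3/2.7 = 4.2, but only against m = 5, which the protocol does not state. Against 0.05/3 the ratio is 11.3/4.4 = 2.6, and against the nominal 5% it is 11.3/5 = 2.3. With a weak effect in 100 mg only, the rate stays below 5%. Liver HU is repeated at visit 5 only in patients with fatty liver (Protocol 7.5.1), so its arms are smaller: at an assumed 10 per arm and 0.6875 SD the rate is about 8%. No single multiple holds.

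**False positives across the eight endpoints.** A reader might add these to the charge. The protocol accepts that error openly, and a correction within endpoints would not remove it, so it is not part of this point.

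**Conclusion.** The discrepancy is real. In the parametric branch, SAP 9.4 departs from the protocol's between-arm adjustment for secondary endpoints, and SAP 12 is inaccurate in declaring no change. The unadjusted rule is adequate if no dose works, with error near 5%. If only 50 mg or only 150 mg works, the error is about 5.5% to 12% per endpoint over 0.25 to 1.5 SD with 24 to 30 per arm (11% at 0.6875 SD and n = 24). The corresponding rates are about 2% to 3% at 0.05/5 and 3% to 4.5% at 0.05/3. If only 100 mg works, the unadjusted range is about 4% to 9%.

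These rates rest on assumed effects, since the documents give none for the secondary endpoints, and on normal data. The textual conflict does not depend on them. These are secondary endpoints in a phase 2 trial, so this is a correction that should be made; it does not threaten the primary result.

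**What to change.** In SAP 9.4, state that the five pairwise comparisons within each secondary endpoint are tested at 0.05/5 = 0.01, or with Bonferroni-adjusted p-values, after ANCOVA and after Kruskal-Wallis alike. State also that there is no adjustment across endpoints, and that no parallel unadjusted t-tests support significance claims. A reference to the primary rule is not enough: SAP 7.7 and 9.3 also allow unadjusted t-tests for TG, and only unadjusted tests after Kruskal-Wallis. Covering the rank-based branch goes beyond the protocol's text, but without it the level would depend on a normality check.

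Alternatively, list the departure in SAP 12 and report unadjusted secondary pairwise results as estimates with confidence intervals, without significance claims.

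Either way, settle it before the SAP is approved, which SAP 6.2 requires before unblinding. The cost is a sentence or two of SAP text, and some secondary p-values become less favourable. With m = 5 behind the gate the rule is somewhat conservative (about 2% to 3%), so some power for true dose differences is lost.
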